1.5 Research Risks & Benefits

1.5.1 Risk of Investigational Device

The risks of rTMS include seizures, headaches, and hearing problems. Since the rTMS induces an electrical field on the brain, the most serious risk is the possibility of having a seizure.

The rTMS coil that is being used in this study is called the "HAC coil". While rTMS has been approved by the FDA for some neuropsychiatric indications such as MDD, this particular coil is experimental and has not yet been approved by the FDA for OCD. Seizures from any kind of rTMS treatment are rare and occur at a rate of about 2/1000. In people who received rTMS in the past with similar intensity and the same Hcoil we will be using in this study, three out of more than 200 people had a seizure. Patients experiencing adverse effects were on certain medications that made them more prone to seizures. In order to minimize the risk for seizures, patients will not be able to participate in this study if they have a medical or psychiatric condition that requires them to take certain medications regularly. Patients will also not be allowed to participate if they have a family history of seizures. A physician will be present during each rTMS treatment and will provide necessary care in case of adverse events. Additionally, suicidal ideation and emergence of manic symptoms following rTMS treatment are also potential risks. Should any of these occur, patients will not be able to continue with the remainder of the study.

There is also a risk of hearing problems (hearing loss or ringing in the ears) after rTMS. This problem is less likely to occur with the proper use of earplugs. The most common risk of rTMS is the possibility of having a headache after the sessions. Over the counter pain medicines (like ibuprofen or acetaminophen) can be taken if needed. Additional risks include scalp and dental pain, which can be treated with over the counter pain medications also. In case of any other adverse events, rTMS will be stopped and patient will be monitored closely.

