1.5.3 Potential benefits

Throughout the course of the study, rTMS may decrease symptoms associated with OCD. rTMS may also ease the patient's ability to engage in cognitive behavior therapy (CBT), which may also help control their symptoms. However there is a possibility of no therapeutic effect for OCD, and therefore there might be no direct benefit to the patient.

As a benefit to the OCD patient cohort, neuroimaging during this study will be used to evaluate rTMS as a screening procedure to help determine which patient populations might derive the most benefit from currently implemented invasive treatment options such as cingulotomy or DBS. Likewise, findings from neuroimaging and EEG will also add to our knowledge of the circuit involved in OCD by assessing acute and longitudinal biomarkers.

2 Study Objectives

The purpose of this study is to understand how rTMS might best benefit patients suffering from disorders of the dACC. In particular, we will determine how rTMS affects patients with OCD. We also aim to evaluate rTMS as a screening procedure to help determine which patient populations might derive the most benefit from currently implemented invasive treatment options such as cingulotomy or DBS. Lastly, we will study how neuromodulation affects the circuitry of the brain by assessing acute and longitudinal biomarkers from neuroimaging.

3 Study Design

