3.2 Primary Safety Endpoints

According to the safety guidelines recommended by Brainsway™ corresponding to the HAC coil, 3 weeks is an acceptable study duration with the investigational HAC-coil. Brainsway™ has performed studies in control subjects and in subjects with clinical conditions (MDD, schizophrenia, bipolar disorder, addiction, PTSD) (Brainsway, Ltd. Unpublished data). They have currently tested 209 subjects (98 without concomitant psychotropic medication; 111 with psychotropic medication) with high-frequency, high-intensity rTMS. Of the subjects who were still taking psychotropic medications that could lower seizure thresholds, 3 suffered a seizure. Should the patient experience adverse effects prior to completion of study, their participation will be discontinued in lieu of their safety. Additionally, we will account for the incidence, severity and frequency of all Adverse Events (AEs), including seizures and suicidality (i.e., suicide attempts and completed suicides).

4 Subject Selection and Withdrawal

CRITERION	METHOD OF ASCERTAINMENT
Inclusion:	
1) Male or female outpatients, 18 to 65 years of age.	Self report
2) Primary diagnosis of Obsessive Compulsive Disorder, as confirmed by the Structured Clinical Interview for the DSM-V-TR (SCID).	SCID, DSM-IV-TR

3) Subjects should have at least a moderate level of OCD severity as defined by a Yale-Brown Obsessive Compulsive Disorder Scale (YBOCS) score of greater than 10 on either obsession section or compulsion section (YBOCS-O \geq 10 or YBOCS-C \geq 10).	YBOCS
3) Patients currently on OCD medication must be at the same stable dose(s) and be willing to continue the same dose(s) through the duration of the study. Note: Subjects should be maintained on SSRI medications (with or without additional antidepressant or psychotropic augmentation for treatment of OCD) at a stable therapeutic dosage for at least 2 months prior to study entry and for the duration of the trial, and/or subjects are maintained on psychotherapeutic behavioral intervention therapy (subjects undergoing CBT treatment must be in the maintenance stage and not in the assessment or skills acquisition or training stages).	Physician Evaluation
4) Patients must continue to be under the care of their treating psychiatrist who will be writing prescriptions for concomitant medications through the duration of the study.	Physician Evaluation
5) Capable and willing to provide informed consent	Physician Evaluation

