13) Intracranial implants (e.g. aneurysm clips, shunts, stimulators, cochlear implants, or electrodes) or any other metal object within or near the head, excluding the mouth, that cannot be safely removed.	Physician Evaluation
14) If participating in psychotherapy, must have been in stable treatment for at least three months prior to entry into the study, with no anticipation of change in frequency of therapeutic sessions, or the therapeutic focus over the duration of the rTMS trial.	Private Psychiatrist Reports
15) Current illicit drug use.	Physician Evaluation and urine drug screen
16) Current significant laboratory abnormality. Note: Clinically significant laboratory abnormality refers to patient lab results that fall outside the established normal ranges, may be indicative of the presence of a medical condition, and are not thought to reflect an artifact or routine lab error (e.g. hemolysis). Results of laboratory tests are reviewed by the study physician prior to any treatment. Abnormal lab results of clinical significance that cannot be resolved (e.g. by repeating the test to rule out laboratory error or poor quality of the original sample) will lead to exclusion from the study.	Physician Evaluation
17) Known or suspected pregnancy.	Urine pregnancy test
18) Women who are breast-feeding.	Self Report
19) Women of childbearing potential not using a medically accepted form of contraception when engaging in sexual intercourse.	Self Report

Patient Discontinuation:

A subject will be discontinued from the study for any of the following reasons:

- Inability to locate and quantify a motor threshold (MT) as defined in the protocol.
- The investigator decides that the patient should be withdrawn for the safety and welfare of the patient. For example, the patient experiences a clinically significant adverse event that is inconsistent with continuation in the study.
- The patient withdraws consent.
- Subject has significant tremor in any limb.
- Subject experiences a seizure.
- Subject has an elevated risk of suicide, based on results from the Columbia Suicide Severity Rating Scale (C-SSRS) and/or psychiatric interview or attempts suicide after receiving rTMS. The study investigator should refer the subject to his/her primary psychiatrist or inpatient hospitalization in case the patient is discontinued from the study.
- Subject becomes pregnant.

The safety of the patient following their discontinuation will be ensured by their primary physician.

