8.2 Recording of Adverse Device Effects

All observed or volunteered adverse effects (serious or non-serious) and abnormal test findings, regardless of treatment group, if applicable, or suspected causal relationship to the investigational device or, if applicable, other study treatment or diagnostic product(s) will be recorded in the subjects' case histories. For all adverse effects, sufficient information will be pursued and/or obtained so as to permit 1) an adequate determination of the outcome of the effect (i.e., whether the effect should be classified as a serious adverse effect) and; 2) an assessment of the causal relationship between the adverse effect and the investigational device or, if applicable, the other study treatment or diagnostic product(s). Adverse effects or abnormal test findings felt to be associated with the investigational device or, if applicable, other study treatment or diagnostic product(s) will be followed until the effect (or its sequelae) or the abnormal test finding resolves or stabilizes at a level acceptable to the sponsor-investigator.

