8.4 Stopping Rules

The patient will be allowed to stop participating in the study at any point. Additionally, any safety considerations will be taken into account and the study will be stopped in accordance with patient comfort. More immediately, rTMS administration will be stopped in the occurrence of any adverse event (See section 4). Regarding the study, we will stop the study if serious AEs are observed in more than 3 subjects.

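### Section 3.2 ends participation for any adverse effect with no severity threshold, so a mild event, if the sentence is followed as written, costs the patient's end-of-treatment imaging and neuropsychology

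*Combined protocol and SAP*

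**What the plan says.** Five places in the combined protocol and SAP deal with what happens after an adverse event.

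- **Section 3.2 (Primary Safety Endpoints):** "Should the patient experience adverse effects prior to completion of study, their participation will be discontinued in lieu of their safety". There is no qualifier for severity, seriousness or relatedness. The next sentence records the severity of all adverse events but does not use it in the rule.
- **Section 1.5.1 (Risk of Investigational Device):** "The most common risk of rTMS is the possibility of having a headache after the sessions", with over-the-counter medicine as the response. It adds: "Additional risks include scalp and dental pain, which can be treated with over the counter pain medications also". For adverse events it has not named, it stops rTMS and has the patient watched closely. After naming suicidal ideation and emergent manic symptoms it says: "Should any of these occur, patients will not be able to continue with the remainder of the study".
- **Section 4 (Patient Discontinuation):** the investigator decides, and the example given is that "the patient experiences a clinically significant adverse event that is inconsistent with continuation in the study". Seizure, significant limb tremor, elevated suicide risk and pregnancy are among the separately listed reasons.
- **Section 5.2 (Treatment Regimen):** intensity may be reduced if the patient cannot tolerate it.
- **Section 8.4 (Stopping Rules):** "rTMS administration will be stopped in the occurrence of any adverse event (See section 4".

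Section 8.2 says that effects thought to be device-related "will be followed until the effect (or its sequelae) or the abnormal test finding resolves or stabilizes". Section 4 leaves safety after discontinuation to the primary physician. Neither section provides for outcome assessments.

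**The concern.** The protocol has no single rule. A patient with a headache after session 3 takes a painkiller and continues under 1.5.1, would normally continue under section 4, and leaves the study under 3.2. No section says which governs.

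What is at stake is the set of measures with only two time points. Section 3.1 makes each patient their own control and compares baseline with the end of the 3-week course. A patient removed before the end has no second value for imaging or neuropsychology. That patient also drops out of the planned correlation of task behaviour with neuroimaging change. This bears on a stated objective, since section 2 says "we will study how neuromodulation affects the circuitry of the brain by assessing acute and longitudinal biomarkers from neuroimaging". Losses of this kind would follow tolerability and so would not be random, and section 7 has no rule for missing end values.

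**Working it through.** **Plan's own figure.** The plan gives 15 subjects with no alpha, power, effect size, SD or dropout allowance, so there is no calculation to reproduce.

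**1. The rules side by side**

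| Event | 3.2 | 1.5.1 | 4 | 5.2 | 8.4 |
|---|---|---|---|---|---|
| Headache, scalp or dental pain | Leaves study | Over-the-counter medicine | Leaves only if the investigator so decides, e.g. clinically significant event | Intensity may be lowered if not tolerated | rTMS stops, but refers to 4 |
| Other mild event | Leaves study | rTMS stops, patient monitored | As above | As above | As above |
| Seizure | Leaves study | Named as most serious risk | Mandatory discontinuation | n/a | rTMS stops |

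On severity, 3.2 conflicts with section 4 and section 5.2, and with 1.5.1 for the three named pains. For other mild events 1.5.1 has no threshold either. The difference there is between stopping treatment and ending participation.

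**2. What has only two time points.** Sections 3.1 and 6 place structural MRI/DTI, simultaneous fMRI-EEG and the neuropsychological evaluations at baseline and end. Section 3.1 lists 9 scales and 10 neuropsychological measures. CGI alone among the scales is repeated during treatment. A patient who leaves early therefore lacks an end value for MRI/DTI, fMRI-EEG, 9 − 1 = 8 scales and all 10 measures.

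**3. What remains.** Number the sessions 1 to 15, Monday to Friday over weeks 1 to 3. From section 6:
- Y-BOCS is on Thursdays: sessions 4, 9 and 14, so 3 in all.
- EEG and CGI are on Tuesdays and Thursdays: sessions 2, 4, 7, 9, 12 and 14. That gives 6 CGI ratings and 6 × 2 = 12 EEG recordings (before and after rTMS).

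| Stop after session | Y-BOCS (of 3) | EEG recordings (of 12) | CGI (of 6) |
|---|---|---|---|
| 3 | 0 | 2 | 1 |
| 5 | 1 | 4 | 2 |
| 10 | 2 | 8 | 4 |

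**4. Effect on precision.** The plan names no paired test. Assume a simple paired mean change with the same SD of change at every n. The 95% CI half-width, in SD units, is t(0.975, n − 1)/√n. For n = 15 this is 2.145/3.873 = 0.554.

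| Pairs | Half-width (SD) | Ratio to 15 pairs |
|---|---|---|
| 15 | 0.554 | 1.00 |
| 14 | 0.577 | 1.04 |
| 13 | 0.604 | 1.09 |
| 12 | 0.635 | 1.15 |
| 10 | 0.715 | 1.29 |

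**5. How many pairs.** The only event rates given are for seizure. Section 3.2 reports 3 seizures in 209 subjects, all among the 111 on psychotropic medication. Carried over to 15 patients, that is 15 × 3/209 = 0.2 or 15 × 3/111 = 0.4 expected seizures, and section 4 removes those patients anyway. Any larger loss must come from mild events, for which no rate is given. As a range on assumed rates only, with every affected patient removed, expected pairs are 15 × (1 − p): 13.5 at 10%, 12 at 20%, 10.5 at 30%, 9 at 40% and 7.5 at 50%. These show how the loss would scale and are not a forecast.

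**The case against.** The strongest reply is that section 4 is the operative withdrawal section and 8.4 points to it. The 3.2 sentence comes directly after the report of three seizures and may have been meant for serious events. Section 5.2 shows that discomfort is to be managed. To withdraw a patient for a headache, the site would have to put 3.2 above sections 1.5.1, 4 and 5.2. Cautious stopping is also defensible for an experimental coil in a 15-patient open-label feasibility study.

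Much of this stands: it makes literal application less likely and leaves the size of the loss unknown. But the sentence is not limited to serious events, and seizure already has its own stop in section 4. Caution about stimulation is a reason to stop rTMS; it is no reason to forgo a final assessment that is safe.

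Two stronger readings are tempting. A reader might infer that 1.5.1 contradicts 3.2 on severity throughout. It does so only for headache, scalp pain and dental pain, because its sentence on other adverse events has no threshold either. A reader might also take 8.4 as a second rule that ends participation for any event. That sentence is loosely worded, but it concerns rTMS administration and refers to section 4.

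**Conclusion.** The point holds as a conflict between stated rules with a conditional cost. If 3.2 is followed as written, a patient with a mild event loses the end-of-treatment MRI/DTI, fMRI-EEG and neuropsychological battery. Each such patient is 1 of 15 pairs (6.7%). Under the paired-mean assumption, one lost pair widens the interval by about 4%, three by 15% and five by 29%. The loss is small for one patient and becomes material only if 3.2 is applied to common mild events.

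Because headache is called the most common risk, a reader might infer that a large share of the 15 pairs will be lost. The documents do not support that: they give no headache rate, and the site may simply apply section 4. Nor does an early stop remove all effectiveness data. Theta, ERPs and Y-BOCS are measured during treatment, and section 3.1 also plans connectivity from EEG sources, so some on-treatment data usually remain. A stop before session 4 leaves no on-treatment Y-BOCS.

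**What to change.** - Use section 4's threshold (clinically significant, investigator's decision) in 3.2, in 8.4 and in the 1.5.1 sentence on other adverse events. If that last sentence is left alone, a mild event outside the three named pains would still stop rTMS.
- State that mild events are handled with over-the-counter medicine or lower intensity.
- Keep every mandatory stop in section 4 and the 1.5.1 stops for suicidal ideation and emergent mania.
- State that stopping rTMS does not by itself end assessments.
- When rTMS stops early, do the planned final battery then, if the patient agrees and it is safe (no MRI if pregnant).
- Record the sessions received, and report early-stop pairs separately from the 3-week pairs.

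The cost is protocol wording and holding an already planned visit earlier for patients who stop. Some automatic stops become investigator judgements, but no named safety stop is weakened. Early-stop measures reflect fewer than 15 sessions and do not restore the 3-week comparison for those patients. The threshold wording is what prevents the loss; the early battery only limits it.

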3.1 General Design

rTMS delivery: High-frequency (10 Hz) deep TMS will be administered at the dACC to patients over 3 weeks using the HAC-coil (Brainsway™ cingulate coil) designed specifically to target the cingulate cortex and the Magstim Rapid stimulator (Magstim Company Limited, Whitland, UK). Sessions will be administered five times a week with a total of 15 visits. The intensity of stimulation will be relative to resting motor threshold (110%). Forty 3-second trains with an inter-train period of 20 seconds will be applied. Total number of pulses administered will be 1200. Periodic weekly behavioral assessments will be performed with the Yale-Brown Obsessive Compulsive Scale (Y-BOCS) to monitor OCD symptoms. We will also test for suicidal ideation (C-SSRS) and monitor manic symptoms (YMRS) twice a week in addition to baseline and at the end of treatment course (x 8 total) and test cognitive function with Minimental status examination (MMSE). Subjects will be compensated for their daily visits in order to offset inconvenience related to time, effort and transportation costs. They will receive \$100 per fMRI session (x2 total) plus \$40 per TMS session (x15 total) over the study period.

Neuropsychological scales and tests: Neuropsychological evaluations will be administered at baseline and at the end of the study.

1. Scales (expected to take 30-40 minutes total):

- USP-Sensory Phenomena Scale

- Hamilton Depression Rating Scale
- Hamilton Anxiety Rating Scale
- Beck Anxiety Inventory
- Beck Depression Inventory, 2nd Edition
- Sheehan Disability Scale
- Barratt Impulsiveness Scale (BIS -11)
- Clinical Global Impression (CGI)
- Quality of Life Enjoyment and Satisfaction- short form (Q-LES)

2. Neuropsychological measures (expected to take about 90 minutes and can be performed in separate sessions as needed):

- Wechsler Abbreviated Scale of Intelligence (WASI)
- WMS-III Faces, LM, Digit Span, Spatial Span, LNS
- Rey Osterrieth Complex Figure (ROCF)
- California Verbal Learning Test, 2nd Edition (CVLT-II)
- Iowa Gambling Test (IGT)
- Wisconsin Card Sort Task (WCST)
- Judgment of Line Orientation
- Boston Naming Test
- DKEFS Verbal Fluency, Trails, Color Word Interference Test
- Grooved Pegs

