5.2 Treatment Regimen

Patients will undergo 3 weeks (5x per week) of high-frequency (10-Hz) rTMS at the dACC interspersed with EEG and neuroimaging acquisitions. The protocol will be administered at the Psychiatric Institute. The intensity of stimulation will be based on resting-motor threshold (RMT). If the patient is unable to tolerate the intensity, this parameter may be reduced to make the patient more comfortable.

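### The primary safety endpoint limits suicidality to attempts and completed suicides, so suicidal ideation, a named risk measured 8 times per patient, is not counted as suicidality

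*Combined protocol and SAP*

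**What the plan says.** Section 3.2 sets the safety endpoint broadly: "we will account for the incidence, severity and frequency of all Adverse Events (AEs"). The sentence then singles out two items: "including seizures and suicidality (i.e., suicide attempts and completed suicides"). Seizures and suicidality are named inclusions within all adverse events. The second is spelled out with 'i.e.', which makes the list of what it covers a closed one.

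Elsewhere the protocol treats ideation as a concern in its own right:

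- Section 1.5.1 states that "suicidal ideation and emergence of manic symptoms following rTMS treatment are also potential risks", and continues: "Should any of these occur, patients will not be able to continue with the remainder of the study".
- Section 3.1 plans the measurement: "We will also test for suicidal ideation (C-SSRS) and monitor manic symptoms (YMRS) twice a week". Two further time points and the total follow: "in addition to baseline and at the end of treatment course (x 8 total").
- Section 4 uses the C-SSRS twice. Exclusion criterion 11 screens out significant acute suicide risk. The discontinuation list removes a patient whose suicide risk is elevated on the C-SSRS and/or at interview, or who attempts suicide after rTMS.
- Section 8.2 has all adverse effects and abnormal test findings entered in the case histories.

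Section 7, the statistical plan, does not mention safety data.

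**The concern.** The outcome labelled suicidality is narrower than the risk the protocol describes and monitors. A patient could develop ideation, be detected by the C-SSRS and leave the trial, and the suicidality count would not change. That patient might appear as a discontinuation or as a general adverse event. Whether the second happens is left to judgement in each case, because no rule links a C-SSRS result to an adverse event.

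At stake is how the safety summary reads. Attempted and completed suicides would be expected to be rare in 15 patients over 3 weeks, so a count limited to them carries little information about whether suicidality worsened. The repeated ideation measurements speak to that question more directly, and they have no stated endpoint or summary.

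**Working it through.** **1. Number of C-SSRS assessments.** Section 3.1 gives 8. Section 5.2 sets the treatment period: "Patients will undergo 3 weeks (5x per week) of high-frequency (10-Hz) rTMS". Twice a week for 3 weeks, plus baseline, plus end of treatment:

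3 × 2 + 1 + 1 = 8, which matches the stated figure.

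The section 6 schedule lists the C-SSRS on Tuesday and Thursday of weeks 1 to 3, which is 6. Its baseline and follow-up rows name no individual scales, so the other 2 are taken to fall there. One of the 8 is baseline, so 8 − 1 = 7 can show a change. In 15 patients (Study Summary) that is up to 15 × 7 = 105 post-baseline assessments.

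**2. Where a case of ideation would be counted.** Take a patient with no attempt whose C-SSRS shows new ideation.

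- Section 1.5.1: the patient does not continue.
- Section 4: the patient is discontinued if the result amounts to elevated suicide risk.
- Section 8.2: the result is recorded in the case history if treated as an adverse effect or abnormal test finding.
- Section 3.2, all adverse events: counted if classed as an adverse event; no criterion is given.
- Section 3.2, suicidality: not counted.
- Section 7: no analysis stated.

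**3. What the narrow definition can show with 15 patients.** The documents give no event rate, so the risk p of an attempt or suicide during the study is an assumption, shown as a range. The chance of at least one event is 1 − (1 − p)^15:

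- p = 0.1%: 1 − 0.999^15 = 1.5%
- p = 0.5%: 1 − 0.995^15 = 7.2%
- p = 1%: 1 − 0.99^15 = 14.0%

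The chance of observing zero is therefore 98.5% at the low end and 86.0% at the high end. A tenfold difference in risk, from 0.1% to 1%, would still give zero in 86% of trials of this size.

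**4. What zero of 15 rules out.** The exact two-sided 95% upper limit is 1 − 0.025^(1/15) = 21.8%. This needs no assumed rate.

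**The case against.** The strongest reply is that the endpoint is all adverse events and the parenthesis describes only one named item in it. Section 8.2 makes recording of abnormal test findings mandatory, and section 3.1 itself speaks of testing for ideation, so a positive C-SSRS result can be read as such a finding. Section 1.5.1 lists ideation and mania among the risks and then turns to other adverse events, which suggests that both are regarded as adverse events. The C-SSRS also drives exclusion and discontinuation.

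Much of this stands. A reader might infer that ideation can never reach the safety data, or that the C-SSRS results go unused. The documents support neither reading: ideation may be counted among the general adverse events, and the scale is used to manage patients. Nor is there a gap in monitoring.

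What the reply does not do is close the gap in the endpoint. An entry in a case history is not an outcome or an analysis. No section says what change in C-SSRS counts as an adverse event. Ideation reported as one would still sit outside suicidality as section 3.2 defines it.

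Two further objections are fair. The attempt rates are assumed, and no rate for new ideation is available either, so this point does not rest on how many cases a wider definition would find. And section 7 is silent on all safety data, not only on the C-SSRS. The C-SSRS differs in that section 3.2 states a definition, and that definition is narrower than the protocol's own account of the risk.

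**Conclusion.** The point holds as a mismatch between the stated definition of suicidality and the risk the protocol names and measures. It rests on the text of sections 1.5.1, 3.1 and 3.2 and does not depend on any assumed rate. The size is illustrative: a 1.5% to 14% chance of any attempt or suicide in 15 patients if the risk is 0.1% to 1%. The 21.8% upper limit for 0 of 15 is exact.

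A reader might go further and infer that the suicidality line is bound to read zero, or that the plan is set up to announce that no suicidality occurred. Zero is likely under the assumed rates but not certain, and no such statement is planned. Widening the definition would also not show that rTMS caused any worsening, because the study is open-label with no reference therapy.

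This should be corrected before safety data are summarised. It is not critical, since patients are monitored and the results are acted on.

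Separately, sections 1.5.1 and 4 give different triggers for ending participation: the first says the occurrence of ideation, the second elevated suicide risk on the C-SSRS and/or at interview, or an attempt. These must be reconciled with each other.

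**What to change.** In section 3.2, replace the parenthetical definition with: *suicidality, defined as any post-baseline worsening from baseline in C-SSRS ideation or behavior category, including attempts and completed suicides.*

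Add to section 7:

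- Report the number of patients with any worsening over the 7 post-baseline assessments, with an exact 95% CI.
- Use all treated patients as the denominator, including those withdrawn early. A visit-by-visit table alone would lose the affected patients after withdrawal.
- Keep attempts and completed suicides as a separate row, so the narrower count remains visible.
- Report post-baseline YMRS worsening in the same table, with the change that counts stated in advance. Section 1.5.1 names manic symptoms alongside ideation, and the YMRS is collected on the same schedule.
- State when a C-SSRS or YMRS change is also recorded as an adverse event.

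The cost is a few lines of text and one extra table from data already scheduled. The safety profile may look slightly less favourable. Sample size, visits, treatment and discontinuation rules are unchanged.
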